5 STUDY ENROLLMENT AND WITHDRAWAL

5.1 Subject Inclusion Criteria

For screening:

- Peripheral *P. falciparum* parasitemia of any density
- Blantyre Coma Score ≤ 2
- No evidence of meningitis on lumbar puncture
- Consciousness not regained after correction of hypoglycemia (if hypoglycemia is present)
- Male or female whose age on the day of screening is between 6 months and 12 years old

If the parents/guardians agree to screening, antimalarial treatment will begin (see Section 6.6), and participants will undergo an ocular funduscopic examination and a brain MRI scan.

Inclusion criteria for randomization:

- Severely increased brain volume on MRI: brain volume score ≥ 6 (see Section 8.2.2.2 for details)
- Willingness to return for follow up visits 1, 6- and 12-months post-randomization

If these criteria are met, guardians will be approached for possible enrollment by a dedicated study nurse or clinician, speaking in the local language (Chichewa).

Antimalarial therapy (standard-of-care) will have already been initiated prior to either of these consent processes

5.2 Subject Exclusion Criteria

Subjects showing evidence of the following at baseline will be excluded from the study:

- Gross malnutrition as evidenced by peripheral edema, hair color changes, or severe wasting
- Advanced Human Immunodeficiency Virus (HIV) disease – defined as known HIV positive status and evidence of severe wasting
- Evidence of recent head trauma by history or physical examination

- Evidence of severe co-morbidity at time of initial evaluation
 - Pneumonia as evidenced by oxygen saturation on room air of <85%
 - Gastroenteritis and shock as evidenced by capillary refill >3 seconds or skin tenting

5.3 Treatment Assignment Procedures

5.3.1 Randomization Procedures

The study will be randomized, but not blinded. Participants will be randomized after completing the eligibility screening procedures. A block randomization scheme will be used to ensure groups of equal size. Blocks sizes of six and nine will be rotated to decrease the predictability of group allocation within a block for data collectors. Children with retinopathy-positive CM will be randomized separately from those with retinopathy-negative CM.

Randomization is based on obtaining a consensus interpretation of brain volume per MRI. If this is not possible for any reason, study participants will be screened but not randomized, and will remain on the PRW. All other study procedures will be followed as described in this protocol.

Randomization is predicated on the risks and benefits as described in this protocol. Endotracheal intubation is required for participants randomized to the “intubation + mechanical ventilation” arm. The current coronavirus pandemic affects the risk/benefit ratio of this arm of the study because endotracheal intubation increases the risk of aerosol spread of the coronavirus (US CDC COVID19 guidance, 4.4.20, www.cdc.gov/coronavirus/2019-ncov/hcp/guidance-risk-assesment-hcp.html). Randomization to the mechanical ventilation arm will be adjusted in accordance with local IRB recommendations during the coronavirus pandemic.

All possible blocks with balanced combinations of group assignment will be documented. Next computer-generated random numbers will be used to select from the balanced blocks. Assignment of study subjects to randomization arm will be performed electronically, through the online data capture mechanism. If Internet service is unavailable at the time of randomization, back up sequentially numbered opaque sealed envelopes prepared before the trial begins will be available. The envelopes will be stored in a secure location with access limited to key study personnel. After a caregiver provides consent for a patient to participate in the study, study arm assignment will first be attempted electronically. If Internet service is unavailable, study personnel will open the next unopened sequentially numbered envelope to reveal the group assignment and dosing calculation sheet.

A master log of all screened and enrolled subjects will be maintained. A subject is considered randomized upon online assignment or opening the envelope to indicate treatment assignment.

Additional subjects may be enrolled into the study at the discretion of the sponsor in the case of any subject who:

- Is randomized but does not receive treatment for any reason
- Has consent for participation in the study withdrawn for reasons other than an adverse event

5.3.2 Masking Procedures

Treatment arms will not be masked.

5.3.3 Reasons for Withdrawal

A study subject will be withdrawn from the study if:

- A screening error is discovered that resulted in incorrect enrollment (subject did not meet inclusion or exclusion criteria)
- CSF from admission lumbar puncture results in growth of pathogenic bacteria
- Parental consent is withdrawn at any stage for any of the procedures or treatment
- It is discovered that the participant has an intercurrent illness that, when combined with the study interventions, might compromise the recovery of the patient
- Safety reasons as judged by the investigator, ISM, or DSMB

5.3.4 Handling of Withdrawals

Participants withdrawn from the study will remain on the PICU/PRW and will continue to benefit from the increased level of clinical care provided. If the participant is withdrawn due to an adverse event (AE; see section 9 below for more details), laboratory monitoring will continue until the event resolves. Participants will continue to have brain volumes evaluated by multiple modalities as long as this is deemed non-injurious. Participants will still be scheduled for a 28-day post randomization follow up visit and measures of neurologic sequelae and brain volume will be collected. If the participant is voluntarily withdrawn from the study by the parent/guardian, all efforts will be made to encourage the participant to return for 28-day post-randomization follow up.

Attempts will be made to recruit additional participants to replace any participants that withdraw prior to reaching the 12-month post-randomization visit. At the conclusion of the study separate analyses will be run on per-protocol and intention-to-treat populations.

5.3.5 Termination of Study

One interim analysis will be carried out as detailed in Section 11.3. Stopping rules related to toxicities attributed to the study agents are delineated in this section. Early study termination is at the discretion of DMID, either of the participating institutional review boards (IRBs), or the DSMB. The investigator will notify the IRB(s) when the study has been completed.

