Variable	OS mean	OS SD	TBS mean	TBS SD	P value
Age (months)	48.25	27.54	59.63	27.88	0.168
Glucose	5.87	2.94	5.63	3.13	0.914 ^d
Hematocrit (%)	23.36 ^a	6.29	25.54	6.97	0.555 ^d
Platelets (*1000/MicroL)	148.9 ^b	373.7	94.3 ^c	176.2	0.993 ^d

OS= observational study (n=48), SD= standard deviation, TBS= treating brain swelling clinical trial (n=16)

^a n=45, ^b n=47, ^c n=15. ^d nonparametric test.

There was no significant difference in admission Blantyre Coma score (p=0.948), sex (p=0.885) or outcome (death/survival, p=0.551) between the 48 children in the observational study and the 16 randomized participants in the Treating Brain Swelling clinical trial.

We therefore conclude that participants enrolled in the observational study (n=48) are comparable to participants randomized to Usual Care (n=16) in the Treating Brain Swelling clinical trial.

We anticipate enrollment in the Usual Care arm in the 2023 season (see below) at a reduced ratio compared to the intervention arms.

Possible future declaration of futility of the ventilation arm:

If we combine the mortality risk in Historical Controls and participants already randomized to Usual Care, the mortality risk of the combined historical control group and children randomized to Usual Care is 36%. At the end of the 2021 season, the mortality risk in the VENT arm was 26.3%. (Five of 19 participants randomized to VENT died or were brain dead.) With only these data, the test of the null hypothesis of a null difference in mortality is not significant (p-value 0.818, 2-sided test).

We believe it likely that VENT will, in the future, be declared futile. If so, randomization of participants enrolled in the Treating Brain Swelling clinical trial after the declaration of futility of VENT would be to HPS or UC. A formal approach to futility assessment for VENT is provided below.

Table 4. Projected enrollment

	2018 – 2021	2022	2023	Total
*Usual care (UC)	64	0	4	68
Ventilatory support (VENT)	19	7	6	32
Hypertonic saline (HPS)	3	14	15	32

*historical controls + study participants enrolled in 2018 and 2019.

Assuming that enrollment in 2023 follows the same trend seen since the beginning of the clinical trial, we will be able to detect a 50% or more risk reduction in either the VENT or HPS arms, compared to UC.

Choice of interventions

The three study arms of the study will be:

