The secondary outcomes include rates of neurological sequelae in all 3 groups; potential surrogate measures of increased intracranial pressure (opening CSF pressure, ONSD measurements from serial ultrasound examinations, NIRS measurements of cerebral oxygenation and muscle reperfusion, serial examinations for papilledema, decreased diastolic flow velocity or increased pulsatility index on TCD, heart rate variability patterns from continuous cardiac monitoring measured from enrollment through initial MRI scan, and standardized clinical observations) and development of hypotension following induction/intubation, defined by proportional deviation from the initial systolic blood pressure at enrollment.

Data collection methods.

The primary outcome will be determined by study clinicians.

For secondary objectives, the following methods will be used:

- ONSD measurements will be collected at the bedside. Data will be transferred to the electronic case report form (CRF).

- TCD measurements will be collected at the bedside. Data will be transferred to the electronic case report form (CRF).
- NIRS will be used to record cerebral oxygenation fluctuations and to measure muscle reperfusion rates after transient occlusion.
- The evolution of heart rate variability and its relationship to clinical status and outcomes will be determined by extracting the archived and time-stamped continuous ECG signal.
- The neurological findings will be captured by clinicians on an electronic case report form (CRF) at the bedside.
- Neurologic status at the 1, 6, and 12-month post-randomization follow-up will be assessed by one of two pediatric neurologists or clinicians trained by them. The Glasgow Outcome Scale (GOS), a global scale for functional outcome that rates patient status into one of five categories (dead, vegetative state, severe disability, moderate disability or good recovery)²⁴⁷ will be used.. Study nurses will administer standardized assessments: The Malawi Developmental Assessment Tool (MDAT) for participants up to the age of 59 months; the Kaufman Assessment Battery for Children, Version II (KABC-II), for participants over the age of 59 months. Both have been validated for use in African children ^{248, 249}.

The details of the techniques involved for the specialized assays (funduscopy, MRI, ONSD, TCD, NIRS, heart rate variability) are included in Section 8 of this Protocol.

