9.6 Safety Oversight (ISM plus SMC or DSMB)

Safety oversight will be under the direction of a DSMB composed of a pediatrician, a pediatric intensivist, a statistician, and others at the discretion of NIAID. The DSMB will meet annually to assess safety and efficacy data on each arm of the study. The DSMB will review aggregate safety data for increased rate of occurrence of serious unexpected adverse reactions. If halting rules are initiated, more frequent meetings may be held. The DMSB will operate under the rules of a DMID-approved charter that will be written at the organizational meeting of the DSMB. At this time, each data element that the DSMB needs to assess will be clearly defined. The DSMB will advise DMID of its findings.

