11.3 Testing the adequacy of randomization

Prior to analysis, the adequacy of the randomization will be evaluated by comparing all baseline characteristics of the three study arms. These variables include characteristics such as age, gender, weight, malarial retinopathy status, height and duration of symptoms prior to admission. Where substantive differences exist in these variables, they may be controlled for in subsequent analyses by regression techniques. The degree of similarity between the study arms will be tested using, as appropriate, ANOVA, nonparametric tests and chi-square tests. However, following Altman²⁵⁹, we will be guided by the degree of dissimilarity rather than strict statistical significance.

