11.6 Interim Analyses

The TBS design is a 4-stage sequential plan to compare VENT to UC on the outcome of mortality. Based on historical controls and initial randomization to UC before 2020, mortality is

assumed fixed at $p_0 = 0.28$. We test the hypothesis that mortality p in VENT is lower, i.e., we test $H_0 : p = p_0$ versus $H_1 : p < p_0$ at significance level $\alpha = .05$. VENT will be declared superior to UC, if we can demonstrate a relative risk reduction of 50% with 80% power. This needs a sample of 38 subjects.

Boundaries for the 4-stage plan are derived from the power family. Early stopping is to reject the null hypothesis. Our first interim analysis was conducted with data from the 2019-2020 malaria seasons. Observed mortality in VENT was 12.5% (2/16). The conclusion was to continue to the next stage. Our current estimate, at the end of the 2021 season is 15.8% (3/19). In accordance with the design, we must continue to the next stage (i.e., 2022 season). The revised boundary information is depicted in the figure.

Figure: Boundary plot at conclusion of stage 2

Legend: The scale is the maximum likelihood estimate (MLE) of the mortality difference (PDIFF), $\theta = p - p_0$ against the actual information level. At stage 1, observed $\theta = 0.125 - 0.28 = -0.155$, and at stage 2, $\theta = 0.158 - 0.28 = -0.122$. The rejection boundaries are not crossed.

Conditional power and predictive power

Conditional power (CP) is the power to reject the null hypothesis $H_0: \theta = 0$ at all future stages given the cumulative interim data. This calculation shows: (a) at the current estimated difference in mortality $\theta = -0.122$, CP=76.1%, (b) at zero difference in mortality, CP=18.6%, (c) at the hypothesized difference, $\theta = -0.14$, CP=82.9%. Predictive power (PP) is the posterior probability

of rejecting the null at the next stage given the current data, assuming a non-informative prior on the mortality difference. PP=66.1% at the current stage.

Based on these assessments it behooves that we proceed to stage 3.

Hypertonic saline (HPS) vs UC

We have our first sample of 3 subjects, one of whom died. Although hardly necessary, a formal analysis provides the exact 95% CI for mortality in HPS, (0.008, 0.906).

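### Section 5.3.5 allows one interim analysis where Section 11.6 runs four stages, and the protocol prints comparative interim results and opposing futility statements in an unmasked trial whose clinicians determine the outcome

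*Combined protocol and SAP*

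**What the plan says.** **Number of looks.** Section 5.3.5 (Termination of Study) states: "One interim analysis will be carried out as detailed in Section 11.3". The section it points to is headed "11.3 Testing the adequacy of randomization" and contains nothing on interim analysis. Section 11.6 states: "The TBS design is a 4-stage sequential plan to compare VENT to UC on the outcome of mortality". It adds: "Boundaries for the 4-stage plan are derived from the power family". It gives a first-look result, shows a boundary plot at the end of stage 2, and concludes: "Based on these assessments it behooves that we proceed to stage 3". Section 11.7 says that the primary test follows from the sequential design in 11.6.

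**Interim results in the protocol body.** Section 11.6 prints VENT mortality of 2/16 and 3/19, one death among three HPS children, conditional power of 76.1%, 18.6% and 82.9%, and predictive power of 66.1%. Section 4 prints five of 19 VENT children dead or brain dead.

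**Futility.** Section 4: "We believe it likely that VENT will, in the future, be declared futile". Section 11.6.1 calls VENT promising and finds that the present evidence does not point to futility.

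**Who sees and who decides.** Section 5.3.2 states that arms are not masked. Section 4 states: "The primary outcome will be determined by study clinicians". Section 9.6 states: "The DSMB will meet annually to assess safety and efficacy data on each arm of the study". The DSMB includes a statistician and advises DMID. Nothing in the documents limits who may see interim comparisons. Section 11.6 gives the decision to continue in the team's own voice and cites no DSMB recommendation.

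**The concern.** There are two linked problems.

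First, the section that governs termination gives a count of looks that the statistical section has already exceeded, and it points to the wrong place. The number of looks is part of what fixes a stopping boundary, so a reader of 5.3.5 and a reader of 11.6 would describe different designs.

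Second, the people who approach families for consent, deliver care and classify outcomes work from a document that tells them how each arm is doing against a benchmark, how likely VENT is to succeed, and what the team expects. Staff in an open trial see individual outcomes anyway. A printed comparison with a benchmark, a conditional power and a futility forecast go further than that. The exposed outcome components are those that need judgement: severe irreversible neurologic failure or brain death in every arm, and ventilatory rescue in HPS and UC. The two futility statements also pull in opposite directions, so the team has no single agreed reading of its own data.

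**Working it through.** **1. The plan's own sample size (11.6).** Inputs: p0 = 0.28, alternative 0.14 (50% relative reduction), one-sided alpha 0.05, power 80%. The one-sample normal approximation with the variance under the alternative gives

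n = (1.645 + 0.842)² × 0.14 × 0.86 / 0.14² = 6.183 × 0.1204 / 0.0196 = 37.98, so 38.

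This matches the stated 38. It is the fixed-sample figure, before any allowance for repeated looks.

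**2. How much the count of looks matters.** The plan names the power family but gives no shape parameter. I therefore assume equally spaced looks and show the range from an O'Brien-Fleming shape to a Pocock shape, at one-sided 0.05 and 80% power.

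| Design | Final critical z | Maximum N |
|---|---|---|
| One interim and a final (5.3.5) | 1.678 to 1.875 | 38.6 to 42.6 |
| Three interims and a final (11.6) | 1.733 to 2.067 | 39.3 to 46.5 |

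The two sections describe different designs. With an O'Brien-Fleming shape the difference is small. With a Pocock shape it is about 4 children (46.5 − 42.6 = 3.9).

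**3. Looks used.** Four stages are 3 interim looks and 1 final analysis. Two interim looks are reported, against the one that 5.3.5 allows.

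**4. Printed results.** 2/16 = 12.5%, 3/19 = 15.8% and 5/19 = 26.3% all agree with the text.

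**5. Why the futility statements can diverge.** Section 4 sets 5/19 (death or brain death) against a combined control mortality of 36%. Section 11.6 sets 3/19 (deaths) against 0.28. To see how much the event count alone matters, I hold p0 = 0.28 and approximate conditional power with a fixed-sample boundary (1.645), N = 38 and the alternative variance:

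CP = Φ[(Z√I₁ + δ(I_N − I₁) − 1.645√I_N) / √(I_N − I₁)], with I = n / (0.14 × 0.86), I₁ at n = 19, I_N at n = 38, and δ the assumed reduction.

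| Events in VENT | Z | CP at current estimate | CP at no difference | CP at 0.14 |
|---|---|---|---|---|
| 3/19 | 1.53 | 77% | 21% | 83% |
| 5/19 | 0.21 | 3% | 2% | 36% |

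The first row is close to the printed 76.1%, 18.6% and 82.9%. The exact figures depend on boundary details that are not given. The second row shows that counting the two further children moves the picture from promising to poor. The two statements must therefore be reconciled on one event definition and one benchmark.

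**6. What can still be protected.** The projected-enrolment table in Section 4 leaves 7 + 6 = 13 of 32 VENT children and 14 + 15 = 29 of 32 HPS children to come after 2021. If the 2022 season was already complete when the text was written, the figures are 6 and 15. The text can be read either way.

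**The case against.** **The count conflict is leftover wording.** This largely stands. Section 11.7 anchors the primary test to 11.6, and no boundary or analysis depends on 5.3.5. A reader might infer that type I error is inflated. Unadjusted testing would give 0.080 at two looks and 0.117 at four, but 11.6 uses adjusted boundaries, so the documents do not support that inference.

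**Staff in an open single-site trial can count deaths themselves.** This is true in part, and it limits the benefit of restricting access. It does not justify supplying the benchmark comparison, the conditional power and a forecast.

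**Allocation is protected.** This stands. Section 5.3.1 assigns arms electronically after consent, with sealed envelopes as backup, so printed results do not let anyone choose an arm. Consent discussions, care and outcome classification remain open.

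**The DSMB already reviews efficacy by arm.** This also stands, and its charter, which is not among these documents, may limit access. A charter cannot protect results printed in the protocol.

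**A reader might infer that one reclassified child decides the VENT result.** Against 0.28, a fixed-sample exact test at n = 32 gives p = 0.033 for 4 deaths and 0.081 for 5. The documents do not support this reading, for four reasons:
- It is not the plan's test, which is sequential with N = 38. A Wald test at n = 32 gives 0.004, 0.027 and 0.090 for 4, 5 and 6 deaths, so the crossing moves.
- It counts deaths, and death is not open to reclassification.
- Rescue is not a failure component in VENT.
- If brain death counts, 5 of 19 have already failed, so 4 of 32 cannot occur.

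**Conclusion.** The concern holds as a conflict within the protocol and an avoidable risk to trial integrity. The count and cross-reference in 5.3.5 are wrong against 11.6. Comparative interim results and opposing futility statements stand in the working protocol of an unmasked trial whose clinicians determine the outcome.

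No figure can be put on the bias. The documents do not show that enrolment, care or classification changed, and because the two forecasts point in opposite directions, even the likely direction is unclear. A reader might take the printed results as proof that the remaining data are compromised, but the text does not go that far. That clinicians read these pages is an inference. It is a reasonable one, since this is the document they work from.

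The boundary range in the check rests on an assumed shape parameter and equal spacing. The conditional-power comparison is an approximation with a fixed-sample boundary.

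**What to change.** 1. Change 5.3.5 to provide for three interim looks and a final analysis as in Section 11.6.
2. From the next look, send arm-level outcomes, boundary plots and conditional power only to the DSMB and its statistician, who advise DMID to continue, stop or declare futility. This builds on the role that Section 9.6 already gives the DSMB.
3. Remove the interim results and the futility forecast from the protocol body, and reconcile Section 4 with 11.6.1 on one event definition and one benchmark. The reconciled assessment should go to the DSMB.

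A comparison of VENT children enrolled before and after disclosure (19 against a projected 13) is not worth adding. The documents do not date the disclosure, and 13 children at 14% to 28% mortality give only about 2 to 4 deaths (13 × 0.14 = 1.8; 13 × 0.28 = 3.6).

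The cost is protocol wording and, if needed, a charter revision. Investigators lose sight of interim comparisons, and what has already been disclosed cannot be recalled.

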Centralization of evaluations: MRI, ophthalmoscopy, ONSD, TCD, EEG, and neuro-checks will be carried out either at the bedside in the PRW/PICU or in the MRI suite.

Safety monitoring: A local independent safety monitoring team (ISM) will be appointed for the study. The team will consist of two local physicians with knowledge of the clinical setting and practices, but without direct involvement with this study. They will be notified of all SAEs and asked to comment on the relatedness of these events to the interventions. They will also be asked to review AEs at the discretion of the local investigators, IRBs, or the Data Safety and Monitoring Board (DSMB).

A DSMB is justified for this study for two reasons: (1) the anticipated mortality in this group of gravely ill children, without adjunctive treatment, is over 30% (2), and serious adverse events have been reported for HPS (Section 2.3.1.2) and assisted ventilation (Section 2.3.1.3). Interventions may result in survival of children who would have otherwise died, and some of these children may be severely neurologically impaired. In a country like Malawi where there is no social support for such children and their families, their survival could create a burden for the family which might worsen stress and social problems.

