9 ASSESSMENT OF SAFETY

9.1 Specification of Safety Parameters

The primary safety parameter for this study is a comparison of survival of the participants in the three treatment arms. In addition, we will be assessing long term neurological sequelae for all participants.

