9.2.3.1 Protocol defined SAEs

CM is a disease with a high mortality rate. Reported mortality rates range from 15 – 30%, with our site having a rate of 18% over the past 25 years. We anticipate the mortality rate in randomization arm 3 will be approximately 37%. All deaths not attributable to the malarial illness will be reported to independent safety monitors, IRBs, and the sponsor as required.

- Death not caused by respiratory arrest secondary to intracranial hypertension.
- Prolongation of existing hospitalization for more than 7 days due to an intervention.
- A life-threatening adverse event that is not part of the study outcomes defined in the study objectives, an attributable to an intervention.

9.2.4 Procedures to be Followed in the Event of Abnormal Laboratory Test Values or Abnormal Clinical Findings

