9.3 Reporting Procedures

9.3.1 Serious Adverse Events

The reporting period for SAEs will be between the time of randomization and the twelve month (± 2 weeks) post-randomization follow up visit.

SAE reporting will be carried out as follows

The study clinician will complete a Serious Adverse Event Form (Appendix D) and SAEs thought to be related to study related procedures will be reported within 24 hours of their recognition, to the independent safety monitor, the IRBs at Michigan State University and the University of Malawi College of Medicine, and the sponsor, unless advised otherwise by the DSMB.

Any AE that meets a protocol-defined serious criterion will be submitted on an SAE form to the DMID Pharmacovigilance Group, at the following address:

DMID Pharmacovigilance Group
Clinical Research Operations and Management Support (CROMS)
[name]
[name]
SAE Hot Line: [name] (US) or [name] (outside US)
SAE FAX [contact] (US) or [name] (outside US)
SAE Email Address: [contact]

Other supporting documentation of the event may be requested by the DMID Pharmacovigilance Group and will be provided as soon as possible.

The DMID medical monitor and clinical protocol manager will be notified of the SAE by the DMID Pharmacovigilance Group. The DMID medical monitor will review and assess the SAE for regulatory reporting and potential impact on study subject safety and protocol conduct.

At any time after completion of the study, if the investigator becomes aware of an SAE that is suspected to be related to study product, the investigator will report the event to the DMID Pharmacovigilance Group, the independent safety monitor, and the IRBs of the University of Malawi and Michigan State University.

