9.5 Halting Rules

The following eventuality would trigger temporary suspension of enrollment until a safety review is convened and further evaluation undertaken:

- Five subjects where current HPS regimen is unable to achieve the target Na⁺ levels of 150-160 mmol/L.
- Any SAE deemed to be related to each of the experimental medical interventions (ventilator support or infusion of 3% hypertonic saline solution).

DMID retains the authority to suspend additional enrollment and study interventions during the entire study, as applicable.

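### Survival is the primary safety parameter, but the protocol states no quantitative excess-mortality guideline for either active arm, its death-reporting passages conflict, and section 5.3.5 points to the wrong place

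*Combined protocol and SAP*

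**What the plan says.** - **Safety parameter (9.1).** "The primary safety parameter for this study is a comparison of survival of the participants in the three treatment arms".
- **Stopping rules (5.3.5).** One interim analysis is announced, with section 11.3 as its source, followed by "Stopping rules related to toxicities attributed to the study agents are delineated in this section". Section 11.3 is headed "Testing the adequacy of randomization" and deals with baseline balance.
- **Sequential plan (11.6).** Four stages, VENT against a fixed usual-care mortality of 0.28, with lower mortality as the alternative: "Early stopping is to reject the null hypothesis". For HPS the section reports one death in three children with an exact confidence interval, and no boundary.
- **Futility (11.6.1).** A conditional-power assessment for VENT, with under 20% given as an example of a small value. Section 11.7 treats it as something that can be triggered.
- **Halting rules (9.5).** Enrolment is suspended pending safety review if five HPS children cannot reach the sodium target, or for "Any SAE deemed to be related to each of the experimental medical interventions". DMID may also suspend enrolment and interventions.
- **Deaths.** Section 9.2.1 does not routinely count death as an adverse event, but makes certain possibly related events leading to death reportable as SAEs. Section 9.2.3 lists death among serious outcomes. Section 9.2.3.1 reports deaths not attributable to malaria and defines the SAE as "Death not caused by respiratory arrest secondary to intracranial hypertension".
- **Independent safety monitors.** Section 4: "They will be notified of all SAEs and asked to comment on the relatedness of these events to the interventions". Section 9.3.1: "SAEs thought to be related to study related procedures will be reported within 24 hours of their recognition", with the independent monitor among the recipients.
- **Oversight (9.6).** The DSMB reviews safety and efficacy by arm each year under a separate charter.

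**The concern.** When mortality is both the efficacy endpoint and the leading safety measure, one expects a stated level of excess deaths that brings the DSMB together. None appears in this protocol. The trigger that could act between annual meetings, the related-SAE halt in 9.5, depends on a causality judgement.

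That judgement is hardest for exactly the deaths that matter. Section 2.1.13 gives respiratory arrest from intracranial hypertension as the apparent final cause of death in this disease, and 9.2.3.1 leaves that mode outside the protocol-defined SAEs. Section 2.4.1.2 names rebound cerebral edema as a known HPS risk; a death from it could plausibly look the same, though that is an inference. Relatedness is assessed by a study clinician (9.2.1.2) in an unmasked trial (5.3.2). If the 9.3.1 wording governs, a death that the site attributes to malaria may not be sent promptly to the people appointed to give a second opinion on relatedness.

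What is at stake is how soon a harmful effect would be examined, chiefly in HPS, where most enrolment lies ahead.

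**Working it through.** **1. The VENT boundary has only a benefit side.** Inputs from 11.6: p0 = 0.28, p1 = 0.14, one-sided alpha 0.05, power 80%. With the variance under the alternative,

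n = (1.645 + 0.842)² × 0.14 × 0.86 / 0.14² = 37.98, so 38.

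This reproduces the plan's 38 as a one-sided, lower-mortality calculation. Even with a deliberately liberal benefit boundary (exact one-sided 0.05 at each of n = 16, 19, 26 and 38), the simulated chance of stopping is 0.26% at a true VENT mortality of 42% and under 0.01% at 56%. The boundary does not respond to harm.

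**2. Futility reacts to excess VENT deaths, but only indirectly.** With t = n/38, v = 0.14 × 0.86, Z = (0.28 − x/n)√(n/v) and mortality difference θ,

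CP = 1 − Φ{[1.645 − Z√t + θ√(38/v)(1 − t)] / √(1 − t)}.

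| Deaths / n | CP at trend | CP at θ = 0 | CP at θ = −0.14 |
|---|---|---|---|
| 3/19, plan | 76.1% | 18.6% | 82.9% |
| 3/19, recomputed | 77.0% | 21.4% | 83.3% |
| 5/19, recomputed | 2.9% | 1.7% | 36.1% |
| 7/26, recomputed | 0.5% | 0.4% | 9.7% |
| 8/26, recomputed | 0.0% | 0.0% | 1.7% |

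The recomputation comes close to the plan's figures without its exact boundary. Here 26 is the VENT total projected for the end of 2022 (19 + 7, Projected enrollment table, section 4). Eight deaths in 26 (31%) would put CP below 20% throughout. So would seven (27%), which is no excess over 28%. The check cannot tell a harmful arm from an ineffective one. It also depends on the count used: 11.6 has 3/19 deaths at the end of 2021, while section 4 has 5/19 died or brain dead.

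**3. HPS has no numeric check.** The same table projects 3 children to 2021, 14 in 2022 and 15 in 2023, so 29 of 32 come after 2021. At the documents' 36% usual-care mortality, 14 × 0.36 = 5.0 deaths are expected in 2022. At an assumed 60%, 14 × 0.60 = 8.4. The protocol attaches no review to either number.

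**4. The reporting passages, side by side.**

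| Question | One passage | Another passage |
|---|---|---|
| Is death serious? | 9.2.3: yes, as an outcome | 9.2.1: not routinely an AE; 9.2.3.1: not if from the expected mode |
| Which SAEs reach the ISM? | Section 4: all, so that the ISM can comment on relatedness | 9.3.1: those thought related, within 24 hours |
| Where are the stopping rules? | 5.3.5: 11.3, one interim analysis | 11.6, four stages; 9.5, halting rules |

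**5. What a simple HPS guideline would do (illustration only).** At n = 10, 17 and 24, take the smallest k with exact P(X ≥ k) ≤ 0.05.

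- Against 36%: 7/10, 10/17, 14/24 (tails 0.031, 0.046, 0.021).
- Against 28%: 6/10, 9/17, 11/24 (tails 0.034, 0.026, 0.047).

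Exact probability of at least one crossing:

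| True mortality | 36% version | 28% version |
|---|---|---|
| 28% | 1.3% | 7.2% |
| 36% | 6.5% | 25.7% |
| 42% | 16.4% | 47.3% |
| 50% | 39.3% | 75.9% |
| 60% | 74.1% | 95.4% |
| 70% | 95.0% | 99.7% |

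At 60%, the 36% version leads to a mean of about 19 of 32 children enrolled. The benchmark must be settled first: 11.6 uses 28%, while section 4 and 11.5 use 36%.

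**The case against.** Real safeguards exist, and three stronger readings go too far.

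- **A reader might infer that nothing can pause an arm.** The documents do not support that. Section 9.5 suspends enrolment for any related SAE, DMID can suspend at any time, and 5.3.5 gives DMID, the IRBs and the DSMB discretion to terminate. For VENT, the futility check would fall to very low values if deaths accumulated.
- **A reader might infer that deaths are hidden from independent review.** Mortality is the primary endpoint (11.4) and the DSMB sees safety and efficacy by arm (9.6), so deaths reach it whatever cause the site assigns. Section 9.2.1 sets a low threshold, possibly related, and covers the risks in 2.4.1.2, including rebound edema. Section 9.3.1 also sends AEs meeting a protocol-defined serious criterion to DMID pharmacovigilance without a relatedness filter, and its 24-hour clause can be read as setting timing, with section 4 setting scope. Section 2.2.2.4.3 says no human data clearly link hypertonic saline to rebound pressure.
- **A reader might infer that toxicity halting rules do not exist, or that most deaths are exempt.** Rules exist in 9.5, so the reference is misdirected. No count of exempt deaths is given; only the expected mode of death is.

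Two further points stand. The DSMB charter is not in the file and may already hold a mortality guideline. The illustrative looks also add limited protection: HPS is projected at 17 (3 + 14) by the end of 2022, when annual review is plausible, so only the look at 10 clearly comes earlier, and it detects 38% at 60% mortality. VENT has already passed 10 and 17.

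None of this supplies a stated mortality criterion in the protocol, and the relatedness halt still rests on the judgement in question.

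**Conclusion.** The point holds in limited form. This protocol states no quantitative excess-mortality guideline for either active arm. VENT has a benefit-only boundary and an indirect, non-binding futility check; HPS has neither, with 29 of 32 children to come. The expected mode of death lies outside the protocol-defined SAEs unless judged possibly related, the passages on reporting to the ISM conflict, and 5.3.5 misstates both the number of interim analyses and the location of the rules.

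The conclusion concerns the protocol text only. It does not claim that the DSMB lacks a criterion, since the charter is unseen, or that either intervention is harmful. The 50% to 70% mortality figures are assumptions, and the boundaries show scale without being recommended values. This is a change that should be made; it does not invalidate the trial.

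**What to change.** 1. In 5.3.5, cite 11.6 (four stages) and 9.5, and either supply the toxicity rules it mentions or delete the sentence.
2. Reconcile section 4 (Safety monitoring), 9.2.1, 9.2.3, 9.2.3.1 and 9.3.1, so that every death, brain death and SAE in a randomised child goes promptly to the ISM whatever the site's causality view. State that the ISM's relatedness assessment can activate the 9.5 review.
3. Settle the usual-care benchmark (28% or 36%) and the VENT count at the end of 2021 (3/19 deaths or 5/19 died or brain dead).
4. Then add to 9.5, or cite from the DSMB charter if it is already there, a non-binding all-cause mortality guideline that prompts DSMB review for HPS, and one for VENT with looks set from its current 19 children. Publish the operating characteristics with it.

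The cost is protocol and possibly charter wording, plus some extra ISM reports. There is a small chance of an unnecessary temporary enrolment pause: for HPS, about 6.5% under the 36% illustration if 36% is right, but about 26% if the 28% version is used and true mortality is 36%. A non-binding harm guideline can only remove efficacy rejections, so it does not inflate the type I error.
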